9.1.8. Treatment Satisfaction

Assessment of treatment satisfaction will be performed using the Treatment Satisfaction Questionnaire for Medication (TSQM-9) and an exit survey including palatability questions. Both are to be completed after the Exit DBPCFC.

The TSQM-9 is a widely used instrument to assess treatment satisfaction with medication in studies where patient reported side effects have a potential to interfere with the objectives of the study. The instrument consists of 9 questions that comprise 3 scales.

Responses to the 9 individual items will be presented using descriptive statistics. The scale scores (effectiveness, convenience, and global satisfaction) will be calculated and summarized using descriptive statistics for the safety population age group 4-17.

The Effectiveness scale includes items 1-3, the Convenience scale includes items 4-6, and the Global Satisfaction scale includes items 7-9. Each scale will be scored as: $100 * [(sum \ of \ non-missing \ responses) \ minus \ the \ number \ of \ non-missing \ responses] \ divided \ by \ the \ maximum \ possible \ score \ of \ the \ sum \ of \ non-missing \ responses$. If more than one item within the scale has a missing result then the scale score will not be calculated.

In addition to the TSQM-9, an exit survey will be performed at study exit. The survey includes questions on study drug palatability, frequency of taking study drug as instructed,

Sponsor: Aimmune Therapeutics, Inc.

Protocol: ARC0004

Version: Version 1.0, 10Jul2019

impact on attending clinic visits, interest in continuing to take study drug, if the subject would recommend the study drug to others, and burden of treatment. Responses to each item will be summarized for the safety population for each type of instrument administered (parent or subject ages 12 and older, and subjects ages 4 to 11 for the drug palatability as appropriate).

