2.2. SECONDARY OBJECTIVES

The secondary objectives of the study are:

- To confirm the safety profile of AR101 as measured by the incidence of adverse events (AEs), including serious adverse events (SAEs).
- To confirm the efficacy of AR101 through reduction in clinical reactivity, measured in a Double-Blind, Placebo-Controlled Food Challenge (DBPCFC) to a cumulative dose of 4043 mg.
- To evaluate subjects' quality of life (QoL) and treatment satisfaction during AR101 treatment on daily and nondaily treatment regimens.
- To evaluate the long-term immunologic effects of AR101 treatment.

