9.1.7. Quality of Life Assessments

Quality of life assessment using the FAQLQ and the FAIM questionnaires will be performed prior to the start of treatment and after the Exit DBPCFC or early discontinuation.

Separate FAQLQ and FAIM instruments are administered based on the subject's age group. Parent versions are also administered for all subjects. Due to differences between the various instruments, separate summaries will be provided by age group and person who completed the questionnaire (i.e., subject or parent).

FAQLQ:

The FAQLQ is a self-report instrument that is intended to assess the effect of food allergy on the subject's quality of life. Evaluations are done by the subject using a different form by age group (8-12 years and 13-17 years) ([Flokstra-de Blok, 2008](#); [Flokstra-de Blok,](#)

Sponsor: Aimmune Therapeutics, Inc.

Protocol: ARC0004

Version: Version 1.0, 10Jul2019

[2009](#)). Evaluations are also done by the parent/caregiver using a different form by age group (4-6 years, 7-12 years, and 13-17 years) ([DunnGalvin, 2008](#)).

Each question is presented on a scale from 0 (not at all) to 6 (extremely) and scored from 1 to 7. The number of items and domains varies by instrument administered. For reporting, the domains for each included form are as follows:

Adult form ≥ 18 –

- a) Allergen Avoidance and Dietary Restrictions
- b) Risk of Accidental Exposure
- c) Emotional Impact
- d) Food Allergy Related Health

Teen form 13-17 –

- a) Allergen Avoidance and Dietary Restrictions
- b) Risk of Accidental Exposure
- c) Emotional Impact

Child form 8-12 –

- a) Allergen Avoidance and Dietary Restrictions (Allergen Avoidance + Dietary Restrictions)
- b) Risk of Accidental Exposure
- c) Emotional Impact

Parent form teen 13-17 –

- a) Social and Dietary Limitations (Dietary Restrictions + Social Restrictions)
- b) Food Anxiety
- c) Emotional Impact

Parent form 7-12 –

- a) Social and Dietary Limitations
- b) Food Anxiety
- c) Emotional Impact

Parent form 4-6 –

- a) Social and Dietary Limitations
- b) Food Anxiety
- c) Emotional Impact

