The FAIM is scored on a 7-point scale from 1 (limited severity perception) to 7 (greatest severity perception). For parent form item 4 (including 1.4, 2.4, and 4) where responses are given from greatest severity perception to most limited severity perception, the scale should be reversed to range from most limited to most severe for scoring purposes. That is, where the question is positively worded as “Effectively treating him/herself...” a response of “Extremely unlikely” should be scored as a 7 rather than a 1.

Domains for the FAIM are to be defined as follows:

Teen and adult form –

- a) Expectation of outcomes (includes items 1-4)
- b) Risk of Accidental Exposure (includes item 5)
- c) Emotional Impact (includes item 6)

Child form –

- a) Expectation of outcomes (includes items 1-4)
- b) Risk of Accidental Exposure (includes item 5)
- c) Emotional Impact (includes item 6)

Sponsor: Aimmune Therapeutics, Inc.
Protocol: ARC0004
Version: Version 1.0, 10Jul2019

Parent form teen –

- a) Parent expectation of outcomes (includes all items on form 1-4)

Parent form 4-12 –

- a) Parent expectation of outcomes (includes items 1.1-1.4)
- b) Child expectations of outcomes (includes items 2.1-2.4)

Domain scores are the arithmetic average of the non-missing items comprising a domain. For child and teen/adult forms, a total score is defined as the arithmetic average of all the non-missing items. For any respondent and form, the domain and total scores should be calculated only if more than half the items comprising that domain/total score have valid responses.

For subjects 4-17, descriptive statistics for domain scores and for non-parent forms the total scores along with their changes from baseline will be tabulated. Data will be summarized for the safety population separately by questionnaire age group and responder (subject or parent).

Listing of the transformed scores, domain scores, and total scores will be provided, sorted by age group, group/cohort, and subject ID.

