10.11. ASSESSMENT OF ASTHMA CONTROL

Assessment of asthma control in asthmatic subjects using the Asthma Control Test (ACT) questionnaire will be performed.

For subjects 12 years old or older, the ACT has 5 questions each recorded on a scale of 1 (least control) to 5 (greatest control). The total ACT is the sum of the 5 scores and ranges from 5 (least control) to 25 (greatest control). A total score of 19 or less indicates asthma is not adequately controlled. Missing data will not be imputed. If any of the 5 questions have a missing response, the total ACT score will not be calculated.

For subjects under 12, there are 4 questions for the subject and 3 questions for the parents to complete. Subject responses range from 0 (least control) to 3 (greatest control). Parent responses range from 0 (every day) to 5 (no days). The sum of all 7 questions will make up the total score. The total ACT score for subjects under 12 will range from 0 (least control) to 27 (greatest control). A total score of 19 or less indicates asthma is not adequately controlled. Missing data will not be imputed. If any of the questions have a missing response, the total ACT score will not be calculated for that subject.

All analyses of the ACT will be performed separately by subject age group (4-11 for subject and parent, 12-17 subjects). Summary statistics of the score for question, total score and change from baseline will be tabulated by visit and group/cohort. A shift table of asthma control (adequate, not adequate, missing) will be summarized by group/cohort at each visit. The number of subjects with completed ACT questionnaires will be used as the denominator for all percentages.

Listing of the results from the questionnaire, including the total score, will be provided, sorted by age group, group/cohort, subject, and visit.

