10.12. ASSESSMENT OF GI SYMPTOMS BY PEES

Subjects who discontinue treatment due wholly or in part to GI AEs will be instructed to complete the Pediatric Eosinophilic Esophagitis Symptom Scores (PEESS v2.0)

Sponsor: Aimmune Therapeutics, Inc.

Protocol: ARC0004

Version: Version 1.0, 10Jul2019

questionnaire ([Martin, 2015](#); [Franciosi, et al., 2011](#)) monthly for 6 months.

The PEESs questionnaire is composed of 20 items investigating the frequency and severity of eosinophilic esophagitis (EoE) symptoms in the last month. The total score consists of all 20 items. The frequency of symptoms is assessed by items 1, 3, 5, 7, 9, 11, 13, 15, 17, 19 and 20, where each item is scored as: 0=Never, 1=Almost never, 2=Sometimes, 3=Often, 4=Almost always. The severity of symptoms is assessed by items 2, 4, 6, 8, 10, 12, 14, 16, and 18, where each item is scored as: 0=Not bad at all, 1=A little bad, 2=Kind of bad, 3=Bad, 4=Very bad. Each item score is transformed to 0-100 as follows: 0=0, 1=25, 2=50, 3=75, 4=100.

The total, frequency total, and severity total scores are computed as the sum of the items divided by the number of items answered. If more than 50% of the items for the calculation of a score are missing, the score will not be calculated.

PEESS results including the frequency total, severity total, and total scores, will be listed.

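### The TSQM-9 scoring formula subtracts the number of answered items from the numerator but not from the divisor, so no scale can reach 100, and the item ranges the divisor needs are not given

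*SAP*

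**What the plan says.** SAP Section 9.1.8 describes the TSQM-9 as nine questions forming three scales of three items each: Effectiveness (items 1 to 3), Convenience (4 to 6) and Global Satisfaction (7 to 9). Each scale score is 100 times a bracketed quantity, the sum of the non-missing responses "minus \ the \ number \ of \ non-missing \ responses". After the bracket closes, this is "divided \ by \ the \ maximum \ possible \ score \ of \ the \ sum \ of \ non-missing \ responses".

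On missing items: "If more than one item within the scale has a missing result then the scale score will not be calculated". A scored scale therefore has three or two answered items.

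The section gives no minimum or maximum for any TSQM-9 item and no range for the resulting scores. For the other questionnaires the SAP does give the coding:

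- FAQLQ (Section 9.1.7): "Each question is presented on a scale from 0 (not at all) to 6 (extremely) and scored from 1 to 7".
- FAIM (Section 9.1.7): "The FAIM is scored on a 7-point scale from 1 (limited severity perception) to 7 (greatest severity perception".
- ACT from age 12 (Section 10.11): "The total ACT is the sum of the 5 scores and ranges from 5 (least control) to 25 (greatest control". The version for under-12s is also set out, with items 0 to 3 for the child and 0 to 5 for the parent.
- PEESS (Section 10.12): "Each item score is transformed to 0-100 as follows: 0=0, 1=25, 2=50, 3=75, 4=100".

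One of the secondary objectives in SAP Section 2.2 is to evaluate "treatment satisfaction during AR101 treatment on daily and nondaily treatment regimens". Satisfaction measured by this questionnaire is a listed secondary endpoint in SAP Section 3.2 and Protocol Section 9.2.2.

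**The concern.** Taking one off the sum for each answered item makes sense if items are coded from 1: a subject giving the lowest answer throughout then scores 0. Multiplying by 100 points to a percentage scale. For the top of that scale to be 100, the divisor must be the largest value the subtracted sum can take. The SAP instead names the largest value of the sum before subtraction, in the same words the numerator uses for that sum. The result is a scale with a floor of 0 and a ceiling that depends on item coding the SAP does not give.

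The questionnaire is completed once, after the Exit DBPCFC, so there is no change from baseline. SAP Section 6.4 plans no formal comparisons. The reported level of each scale, and the difference a reader sees between daily and nondaily cohorts, are therefore the result itself. Both would be compressed, and a reader who takes the scores as 0-100 would understate satisfaction.

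The quality control in SAP Section 14 relies on a second person programming from the same specification. Two programmers who both follow the sentence literally would agree on the same compressed score.

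**Working it through.** **Inputs**

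- S: sum of the answered items in a scale (SAP 9.1.8).
- n: number of answered items, 3 or 2 under the missing-item rule (SAP 9.1.8).
- M: largest possible S over the answered items. It needs item maxima, which neither document gives. Assumption for the figures below: items coded 1 to K, with K from 4 to 10. K = 7 is the coding the SAP gives for the FAQLQ and FAIM.

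The SAP states no TSQM-9 figure, so there is nothing to reproduce first.

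**Formulas**

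- As written: 100(S − n)/M.
- Minimum removed from both parts: 100(S − n)/(M − n).
- Ceiling as written, at S = M: 100(M − n)/M = 100(1 − n/M). This is below 100 whatever the coding.
- Ratio of the two scores: (M − n)/M.

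**Ceiling with equal item ranges.** With M = nK, the ceiling is 100(nK − n)/(nK) = 100(K − 1)/K. It does not depend on n.

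| K | Ceiling as written | 10 points on a 0-100 scale shown as |
|---|---|---|
| 4 | 75.0 | 7.5 |
| 5 | 80.0 | 8.0 |
| 6 | 83.3 | 8.3 |
| 7 | 85.7 | 8.6 |
| 8 | 87.5 | 8.8 |
| 9 | 88.9 | 8.9 |
| 10 | 90.0 | 9.0 |

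Mid-range answers throughout score 37.5 (K = 4) to 45.0 (K = 10) as written, and 50 with the second formula. At the floor, S = n, both formulas give 0.

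**Worked scores**

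- K = 5, n = 3, S = 12: 100 × 9/15 = 60.0 as written; 100 × 9/12 = 75.0 with n removed from both parts.
- K = 7, n = 3, S = 15: 100 × 12/21 = 57.1; 100 × 12/18 = 66.7.
- K = 5, one item missing, n = 2, S = 8: 100 × 6/10 = 60.0; 100 × 6/8 = 75.0. The factor is the same, 0.80.

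**Unequal item ranges.** Assume maxima of 5, 5 and 7 within one scale.

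- All answered: 100(17 − 3)/17 = 82.4.
- One 5-point item missing: 100(12 − 2)/12 = 83.3.
- The 7-point item missing: 100(10 − 2)/10 = 80.0.

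Here the compression differs between subjects according to which item is missing. It would likewise differ between scales whose item ranges differ. The second formula gives a ceiling of 100 in every one of these cases.

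**Coding from 0.** If three items were coded 0 to 4, the formula as written would run from 100(0 − 3)/12 = −25.0 to 100(12 − 3)/12 = 75.0. Coded 0 to 6, it would run from 100(0 − 3)/18 = −16.7 to 100(18 − 3)/18 = 83.3. The ceiling stays below 100, and the negative floor suggests that coding from 1 was intended.

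**The case against.** The best case for the plan is that the sentence is loosely worded rather than wrong. The divisor could be meant as the maximum of the whole bracketed difference, which would give 0-100, and no sentence in either document says that a TSQM-9 scale runs to 100. The item codes would normally be on the questionnaire or case report form, which is not part of the documents. The SAP also leaves item detail to the instruments elsewhere: it names the FAQLQ domains without listing their items. The impact is small: there is one assessment, no formal comparison and no decision that uses the score. Within a scale with complete responses the effect is a constant factor, and all nine items are also summarised individually.

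Much of this stands. The 0-100 target is an inference, the intended divisor may well have been the correct one, and the impact is modest. The missing item ranges alone would be only an omission of detail. The benign reading, however, requires replacing the words the SAP uses, since the divisor names the sum of the responses and not the difference. No other section corrects it. A scoring rule that must be reworded to give the intended scale should be corrected in the text.

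**Conclusion.** The point holds. Followed as written, the formula gives every TSQM-9 scale a ceiling below 100; this needs no assumption about item coding. The size does: for items coded 1 to K with K from 4 to 10, the ceiling is 75.0 to 90.0, and absolute differences between cohorts shrink to between 75% and 90% of their value on a 0-100 scale. That the scale was meant to run from 0 to 100 is inferred from the factor of 100 and the subtraction of n.

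The consequence is limited to the reported level and absolute differences of a descriptive secondary endpoint. Ordering and standardised differences within a scale are unchanged when responses are complete. The factor varies between scales, or between subjects with one missing item, only if item ranges differ. The item-level summaries and the exit survey do not use the formula. The correction should be made because the rule is wrong as stated and cheap to put right.

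**What to change.** In SAP Section 9.1.8:

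1. State the minimum and maximum code of each TSQM-9 item.
2. Define the divisor as the maximum possible sum of the answered items minus the number of answered items. This is right if items are coded from 1. If they are not, subtract the sum of the item minima in both numerator and divisor.
3. State that each scale runs from 0 to 100.

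The cost is one or two lines of SAP text and one line of code. Nothing changes for patients or data collection, and any scores already derived can be recomputed from the item responses. The correction should be made in the SAP and not only in code, because SAP Section 11 requires true differences in analysis methods from the plan to be documented.

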9.2. INTERIM ANALYSIS

There is no interim analysis of efficacy planned for this study.

10. SAFETY

Safety will be assessed based on extent of exposure, concomitant medications, physical examinations, and all the safety endpoints defined in [Section 3.2](#).

Unless otherwise noted, safety data will be summarized descriptively and the Safety population will be used for all summaries of safety parameters. Event data such as adverse events will be summarized by study period in 2 parts. Part 1 includes Group 1 study periods of IDE and updosing, maintenance, and overall and Group 2 Cohort 2 periods of QOD, BIW, and overall. Part 2 includes all Group 2 QD AR101 rollovers and summarizes by Cohort 1, Cohort 3A, combined Cohorts 3B and 3C (and their respective periods of QD, QOD, BIW, and Overall), and Overall QD representing all Group 2 QD. In general, safety data will be summarized for age group 4-17 years. Additionally, key safety tables will be presented for 18-55 year old subjects. Safety listings will include all treated subjects, sorted by age group and group/cohort.

10.1. STUDY TREATMENT EXPOSURE

Study treatment exposure will be summarized by age group (ages 4 to 17 and 18 to 55), group/cohort, and study period. The calculation of exposure will be based on in clinic dosing data and the dose level of the dispensed study medication.

First and last dose dates for each study period will be identified as follows:

| Study Period | Group/ Cohort | First Dose Date | Last Dose Date |
|-------------------------|--------------------------------|-----------------------------------------------------------------------------------------|----------------------------------------------------------------------------------------------------------------------------------------------------------------------------------------------------------------------------------------------------------------------------------------|
| Initial Dose Escalation | Group 1 | Date of first in-clinic dose at Initial Dose Escalation Day 1 | Date of last in-clinic dose at Initial Dose Escalation Day 1 or Day 2 |
| Up-Dosing | Group 1 | The day following the date study product was dispensed at Initial Dose Escalation Day 2 | Date of first in-clinic dose of 300 mg at the End Up-Dosing 300 mg Visit. For subjects who do not reach the 300 mg dose: the latest of the last in-clinic dose during the Up-Dosing period or the date of last study drug administration as entered on the Early Termination CRF page. |
| Maintenance | Group 1 | The day following the date study product was dispensed at End Up-Dosing 300 mg Visit | Latest of the last in-clinic dose during the Maintenance period or the date of last study drug administration as entered on the Early Termination CRF page |
| QD | Group 2, Cohorts 1, 3A, 3B, 3C | The first day of AR101 therapy in study ARC004 while on QD dosing | The last day of AR101 therapy in study ARC004 while on QD dosing |
| QOD | Group 2, Cohorts 2, 3B, and 3C | The first day of AR101 therapy in study ARC004 while on QOD dosing | The last day of AR101 therapy in study ARC004 while on QOD dosing |

Sponsor: Aimmune Therapeutics, Inc.

Protocol: ARC0004

Version: Version 1.0, 10Jul2019

| | | | |
|-----|--------------------------------------|--------------------------------------------------------------------------|----------------------------------------------------------------------|
| BIW | Group 2, Cohorts 2, 3B, and 3C | The first day of AR101 therapy in study ARC004 while on BIW dosing | The last day of AR101 therapy in study ARC004 while on BIW dosing |
|-----|--------------------------------------|--------------------------------------------------------------------------|----------------------------------------------------------------------|

The total amount of study product consumed will be calculated as the sum of in-clinic doses plus the sum of doses taken at home as recorded in the diary.

The following calculations of study product exposure will be made and summarized:

- Duration of Exposure (in days and in months): calculated as the date of last dose of study product minus the date of the first dose of study product plus one during the study period. Duration of exposure will be summarized using descriptive statistics as well as categorically by the expected lengths of the overall treatment period.
- Total dose consumed (mg): calculated as the cumulative sum of all doses taken during the study period.
- Average dose per day (mg): calculated as the total dose consumed divided by the number of days during the study period.
- For Group 1 only: Maximum dose achieved (mg/day) during up-dosing using descriptive statistics for continuous data as well as categorically using all possible dose levels: 0.5, 1, 1.5, 3, 6, 12, 20, 40, 80, 120, 160, 200, 240, or 300 mg/day.
- For Group 1 only: Time to 300 mg dosing and time to 80 mg dosing for the overall treatment period using Kaplan-Meier methodology. Time will be calculated as date of the first 300 mg (or 80 mg) dose minus the first dose date +1. Subjects who do not reach the specified dose will be censored at the date of their last study product dose.

The non-missing valid diary entries will be used to estimate at-home dosing compliance. The following measures of compliance with at-home dosing will be calculated:

- Total number of planned at-home dosing days: calculated as the number of days where a valid diary entry was made, but excluding entries where a dose was missed because of doctor's orders.
- Percentage of planned dosing days where a full or partial dose was consumed.
- Percentage of planned dosing days where a full dose was consumed.
- Percentage of planned dosing days where a partial dose was consumed.
- Percentage of planned dosing days where a dose was missed.

Sponsor: Aimmune Therapeutics, Inc.

Protocol: ARC0004

Version: Version 1.0, 10Jul2019

At-home dosing data will be listed. Daily diary records, including date and time, whether a full or partial dose was consumed (or the dose was missed), reason for partial or missed dose will be listed.

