Abbreviations: ACT = Asthma Control Test; AEs = adverse events; AEIs = adverse events of interest; BP = blood pressure; CBC = complete blood count; CRC = clinical research center; DBPCFC = double-blind, placebo controlled food challenge; FAIM = food allergy independent measure; FAQLQ = food allergy related quality of life questionnaire; FEV₁ = forced expiratory volume in 1 second; GI = gastrointestinal; Ig = immunoglobulin; OIT = oral immunotherapy; PEESS = Pediatric Eosinophilic Esophagitis Symptom Scores; PEFR = peak expiratory flow rate; PR = pulse rate; temp = body temperature; TSQM-9 = Treatment Satisfaction Questionnaire for Medication; wks = weeks

Footnotes:

- Subjects who have the option to switch to AR101 daily in ARC008 may start AR101 daily dosing (Repeat Up-dosing from 80, 120, or 160 mg to 300 mg daily) and have visits in ARC004 if ARC008 is not yet available at the study site ([Section 3](#)). Repeat Up-dosing may be up to a maximum of 26 weeks.
- Any of the procedures performed at CRC dosing visits (except Post-Maintenance DBPCFC) may be performed at unscheduled visits.

- c) Day 1 of the Initial Escalation Period will be scheduled within 10 days after the ARC003 Exit DBPCFC. See [Table 1](#) for dose escalation schedule. Subjects will begin home dosing at dose 3 mg/d on Day 3.
 - Day 1: Escalation to ≥ 3 mg or 6 mg, as tolerated (subjects who cannot tolerate 3 mg are escalation failures).
 - Day 2: Confirm tolerance of 3 mg. Day 2 should occur on the next consecutive day following Day 1.
- d) Subjects return to clinic every 2 weeks for up-dosing to a maximum of 300 mg, following the dose escalation schedule in [Table 2](#), unless up-dosing is delayed due to allergic reaction. The Up-dosing Period ends after maintaining the 300-mg dose for 2 weeks.
- e) CRC dosing occurs at Weeks 12 and 24 after entering the Maintenance Period, with a Post-maintenance DBPCFC at Week 24 (approximately).
- f) Physical examination to include height and weight. At the investigator's discretion, limited or symptom-directed physical examinations may be completed in CRC dosing visits during the Extended Maintenance Period. Full physical examinations are to be conducted at the Screening/Baseline, 80 mg Up-dosing Visit, End of Up-dosing/Maintenance Visit 1 (2 weeks at 300 mg), and the Exit/Early Discontinuation visits.
- g) End of Up-dosing/Maintenance Visit 1 physical examination will be a complete physical examination and will include height and weight.

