- u) Telephone follow-up will occur 6 weeks before and after each scheduled Initial Maintenance visit to inquire about allergic symptoms and promote compliance.
- v) Subjects who fall into any of these 3 categories will be asked to fill out the PEESS v2.0 questionnaire ([Franciosi et al, 2011](#)), with the assistance of a parent or guardian, as appropriate, every month for 6 months:
 - Any subject whose dose is withheld for > 7 days due to GI AEs and resumes dosing at a reduced dose level ([Section 7.3.3.2](#)).
 - Any subject who develops chronic/recurrent GI AEs at or before reaching the 20-mg dose level and resumes dosing after a 30-day dosing hiatus ([Section 6.5.3.2](#)).
 - Any subject who permanently discontinues dosing who had experienced GI AEs ([Section 7.3.3.2](#)).
- w) Subjects should not administer their AR101 dose on days when DBPCFC is conducted.
- x) For group 1 subjects only. Perform before the Post-Maintenance DBPCFC at the end of Initial Maintenance.

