7.5. DATA DERIVATIONS AND DEFINITIONS

The following definitions and derivations will be used throughout this study:

- Study day is calculated relative to the first dose date in ARC004 as (assessment date – first dose date + 1) for assessments and visits performed on or after the first dose date, and (assessment date – first dose date) for assessments and visits prior to the first dose date.
- In this follow on study, baseline is defined as the last non-missing value prior to the first dose of study treatment in the study where study product is first received. For Group 1 patients (those previously on placebo in ARC003), baseline is relative to first dose of AR101 in study ARC004. For Group 2 patients (those continuing on AR101 therapy from ARC003), baseline is relative to first dose of AR101 in study ARC003. If no ARC004 data were entered for a Group 1 subject, use the last available ARC003 data prior to first dose of AR101 in ARC004. For food challenge end points, the ARC003 exit food challenge will serve as the baseline for both groups.

Sponsor: Aimmune Therapeutics, Inc.

Protocol: ARC0004

Version: Version 1.0, 10Jul2019

- Change from baseline is calculated as observed value after the first dose – baseline value.
- Group 1 Initial Dose Escalation period is defined as the time period beginning with the date and time of the first dose of study product in clinic and ending with the date of the last dose of study product taken prior to Up-dosing.
- Group 1 Up-dosing period is defined as the time period beginning with the date and time of the first home dose of study product at 3 mg, and ending with the date and time of first in-clinic dose at 300 mg. This period will be, ideally, 22 weeks in duration, but may be extended to a maximum of 40 weeks to accommodate dose reductions and re-escalations, if necessary.
- Group 1 Maintenance period is defined as the time period beginning with the date and time of the first home dose of study product at 300 mg and ending with the date of the last dose of study product taken prior to the maintenance DBPCFC. The maintenance period lasts approximately 24 weeks.

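### The Group 1 Maintenance row in SAP 10.1 ends exposure at the last clinic dose or the Early Termination date, which contradicts SAP 7.5 and does not match the pooled period of SAP 6.1

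*SAP*

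**What the plan says.** SAP 7.5 introduces its list with "The following definitions and derivations will be used throughout this study". There, Group 1 Maintenance starts at the first home dose of 300 mg, "ending with the date of the last dose of study product taken prior to the maintenance DBPCFC", and the length is given: "The maintenance period lasts approximately 24 weeks". EM for Group 1 starts at the first dose after that challenge and stops at the last dose before the Exit DBPCFC.

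The table in SAP 10.1 starts Group 1 Maintenance on "The day following the date study product was dispensed at End Up-Dosing 300 mg Visit", which agrees with 7.5. It ends it at the "Latest of the last in-clinic dose during the Maintenance period or the date of last study drug administration", the second date being taken from the Early Termination CRF page. Other features of the same table matter:

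- The Up-Dosing row also uses the Early Termination date, but only with a restriction: "For subjects who do not reach the 300 mg dose: the latest of the last in-clinic dose during the Up-Dosing period" or that date. The Maintenance row carries no restriction to subjects who stopped in the period.
- There is no EM row for Group 1.
- The Group 2 rows end on the last day of therapy on the regimen and do not mention clinic doses.

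SAP 10.1 then defines duration as last dose date minus first dose date plus one. Total dose is clinic doses plus diary-recorded home doses, and average daily dose is total dose over days in the period. SAP 10.3 divides events by subject-years at risk in the period and does not say which dates supply them.

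SAP 6.1 sets the Group 1 columns for event summaries and puts Maintenance and EM into one QD column. SAP 11 does not list any of this as a change.

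In the protocol, section 3.1.4 and Appendix 1-A footnote e place clinic dosing at Weeks 12 and 24 of Maintenance and the challenge at about Week 24. Footnote w says "Subjects should not administer their AR101 dose on days when DBPCFC is conducted". Section 3.1.5 spaces Group 1 EM visits 14 weeks apart, and section 6.8 allows a challenge visit to fall within 2 weeks of schedule.

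**The concern.** Two end rules for a period of the same name cannot both be followed. Most 300 mg doses in this period are taken at home, so a rule tied to clinic doses discards whatever is taken between the last clinic dose and the end of the period. The unrestricted Early Termination date acts the other way: for someone who passes the maintenance challenge and stops later, it is the later of the two dates, and it lies in EM.

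The figures at stake are the Group 1 duration of exposure, the average daily dose and, if these dates are used for time at risk, the exposure-adjusted rates. Those rates include treatment-related AEs, the event type of the primary endpoint. On the stand-alone reading, EM time of Group 1 completers also has no row in the exposure table.

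**Working it through.** No power or sample-size figure is involved. The only stated figure is the length of about 24 weeks.

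**Inputs.** On-schedule visits are assumed. Day 0 is the first clinic dose of 300 mg and day 1 the first home dose. Maintenance Visit 1 is day 14 (about 2 weeks later, protocol 6.3.6). Week 12 is 14 + 84 = day 98 and Week 24 is 14 + 168 = day 182. Duration = last − first + 1 (SAP 10.1).

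**Stated length.** From Maintenance Visit 1 to the day before a Week 24 challenge: 181 − 14 + 1 = 168 days = 24.0 weeks, which agrees. From the SAP's own start: 181 − 1 + 1 = 181 days = 25.9 weeks, because the SAP clock starts about two weeks earlier.

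**Reading 1: the row is Maintenance alone. Completers without an Early Termination date.**

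| Situation | SAP 7.5 | SAP 10.1 | Lost |
|---|---|---|---|
| Week 24 clinic dose, challenge next day | 182 | 182 | 0 |
| Week 24 clinic dose, challenge 7 days later | 188 | 182 | 6 (3%) |
| Week 24 clinic dose, challenge 14 days later | 195 | 182 | 13 (7%) |
| Week 24 visit is the challenge day, no clinic dose | 181 | 98 | 83 (46%) |

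In the last row, a rate for that subject using the 10.1 dates would be 181/98 = 1.85 times as high. With full adherence at 300 mg, dividing every diary dose of the 7.5 period by the truncated days gives 181 × 300 / 98 = 554 mg per day on a 300 mg regimen. If the diary doses are cut at day 98 as well, the average is correct but the total dose falls from 181 × 300 = 54,300 mg to 98 × 300 = 29,400 mg.

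**Reading 1: subjects who stop in EM.** The time from challenge to last dose is an assumed range, against 181 days under 7.5.

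- 14 weeks: 182 + 98 = 280 days, 1.5 times
- 28 weeks: 182 + 196 = 378 days, 2.1 times
- 56 weeks: 182 + 392 = 574 days, 3.2 times

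**Reading 2: the row is Maintenance plus EM.** EM time is now intended. Take a completer with no Early Termination date whose last clinic dose is one 14-week visit before Exit, since no AR101 is given on the challenge day. EM lengths of 28 and 56 weeks are assumed.

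- 28 weeks: last dose day 182 + 196 − 1 = 377, last clinic dose day 182 + 98 = 280. Lost: 97 days (97/377 = 26%).
- 56 weeks: last dose day 182 + 392 − 1 = 573, last clinic dose day 182 + 294 = 476. Lost: 97 days (97/573 = 17%).

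**The case against.** The best defence is that the row was meant as the pooled period. SAP 6.1 combines Group 1 Maintenance and EM, SAP 10.5 groups the 300 mg QD maintenance and extended maintenance dose, SAP 2.3 records that Group 1 subjects on QD were to stay on QD, and the exposure table has no Group 1 EM row. On that view, running to the Early Termination date is correct for an EM dropout, and a completer has clinic doses in EM, so nothing stops at Week 12. This largely stands as a possible intention, but 10.1 does not say it. The row also keeps the name that 7.5 defines otherwise, and the loss of home doses after the last clinic dose remains.

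A second defence is that 10.1 opens by basing exposure on clinic dosing and the dispensed dose level, so the anchor may be deliberate. But the same section counts diary doses in the total, and the Group 2 rows do not use clinic doses as the end point.

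Third, the Week 12 stop is not the scheduled case. Observed dosing is planned at Week 24, and unscheduled clinic doses are possible. This stands: the 46% loss needs the Week 24 clinic dose to be absent, and the documents do not show how often that happens.

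Fourth, subject-incidence tables do not use these durations, and the SAP plans no formal comparisons. This also stands.

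**Conclusion.** The row needs correcting under either reading. As Maintenance alone, it drops 0 to 13 days for a completer with a Week 24 clinic dose within two weeks of the challenge, 83 of 181 days for one without that dose, and credits EM time to those who stop in EM. As the pooled period, it drops up to about 97 days for a completer with no Early Termination date. Duration of exposure is affected directly. Average daily dose is affected when diary doses and days follow different end dates. Exposure-adjusted rates are affected only if their subject-years come from this table.

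A reader might infer that Group 1 Maintenance rates are biased in opposite directions, too high for completers and too low for later dropouts. The documents do not establish that. SAP 6.1 pools the events of both periods, so the dropout half may not be an error, and SAP 10.3 does not tie time at risk to these dates. Nor should 1.85 be read as the effect on the cohort; it is the figure for one subject in the worst case.

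The day counts assume on-schedule visits, and the EM durations are assumptions. The CRF is not among the documents. If the Early Termination page is completed for every subject, the row runs into EM for everyone who entered it, and the loss for completers disappears.

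**What to change.** In SAP 10.1, base the Group 1 end dates on the last dose taken, whether in clinic or recorded in the diary, and choose one of two forms:

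- **(a) Separate rows.** End Maintenance at the last dose before the maintenance DBPCFC, as in 7.5, and use the Early Termination date only for subjects who stop before that challenge. Add a Group 1 EM row ending at the last dose before the Exit DBPCFC or at early termination. Sum the two rows for the pooled period of 6.1.
- **(b) One pooled row.** Rename it to show that it covers all QD maintenance including EM, and end it at the last dose before the Exit DBPCFC or at early termination.

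Shortening the existing row to the 7.5 end date without adding the EM row is not enough. If its dates fed the rates, EM time would leave the denominator of the pooled column while EM events stayed in the numerator.

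Add one sentence to SAP 10.3 stating that the same period dates assign events and give subject-years at risk.

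The cost is one or two table rows and a sentence in the SAP, plus the matching derivation. Diary dose dates are already collected and listed, so no new data are needed.
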